5.4.1.3.8. Procedures for Other Immune-Mediated Adverse Reactions, Including Ocular Manifestations

Epacadostat and pembrolizumab should be permanently discontinued for severe immune-mediated adverse reactions. Systemic corticosteroids treatment should be initiated at a dose of 1 to 2 mg/kg per day of prednisone or equivalent for severe immune-mediated adverse reactions.

Corticosteroid eye drops should be administered to subjects who develop uveitis, iritis, or episcleritis. Epacadostat and pembrolizumab should be permanently discontinued for immune-mediated ocular disease that is unresponsive to local immunosuppressive therapy.

5.4.2. Treatment After Initial Evidence of Radiographic Disease Progression

Immunotherapeutic agents such as pembrolizumab and epacadostat may produce antitumor effects by potentiating endogenous cancer-specific immune responses. The response patterns seen with such an approach may extend beyond the typical time course of responses seen with cytotoxic agents and can manifest as a clinical response after an initial increase in tumor burden or even the appearance of new lesions.

If radiographic imaging shows PD, tumor assessment should be repeated 2 to 4 weeks and no later than 8 weeks after the initial assessment to confirm PD, with the option of continuing treatment as outlined below, while awaiting radiographic confirmation of progression. If repeat imaging shows a reduction in the tumor burden compared to the initial scan demonstrating PD, treatment may be continued as per treatment calendar. If repeat imaging confirms PD, subjects will be discontinued from study therapy. In determining whether the tumor burden has increased or decreased, investigators should consider all target lesions as well as nontarget lesions.

When feasible, subjects should not be discontinued until progression is confirmed; however, the decision to continue study treatment after the first evidence of disease progression is at the investigator's discretion based on the clinical status of the subject as described in [Table 26](#).

Subjects may receive study treatment while waiting for confirmation of PD if they are clinically stable as defined by the following criteria:

- Absence of signs and symptoms (including worsening of laboratory values) indicating disease progression.
- No decline in ECOG performance status.
- Absence of rapid progression of disease.
- Absence of progressive tumor at critical anatomical sites (eg, cord compression) requiring urgent alternative medical intervention.

Table 26: Imaging and Treatment After First Radiographic Evidence of Progressive Disease

	Clinically Stable		Clinically Unstable	
	Imaging	Treatment	Imaging	Treatment
First radiographic evidence of PD	Repeat imaging at 4 and 8 weeks to confirm PD	May continue study treatment at the investigator's discretion while awaiting confirmatory scan	Repeat imaging at 4 and 8 weeks to confirm PD if possible	Discontinue treatment
Repeat scan at 4 and 8 weeks confirms PD	No additional imaging required	Discontinue treatment	No additional imaging required	N/A
Repeat scan at 4 and 8 weeks shows SD, PR, or CR	Continue regularly scheduled imaging assessments every 9 weeks	Continue study treatment at the investigator's discretion	Continue regularly scheduled imaging assessments every 9 weeks	May restart study treatment if condition has improved and/or clinically stable per investigator's discretion

543. Procedures for Subjects Exhibiting Serotonin Syndrome

As noted in Section 1.8.1, there is a rare possibility that epacadostat could cause an increase in serotonin levels in the brain that might trigger SS (Boyer and Shannon 2005) when administered in combination with other serotonergic agents. This syndrome has been most closely associated with the use of MAOis, meperidine, tramadol, linezolid, or methylene blue; all of these agents are prohibited during the study. Selective SSRis and serotonin-norepinephrine reuptake inhibitors (SNRIs) are permitted during the study. The following procedures will be implemented if subjects exhibit the signs/symptoms of SS (Table 27), including tremor, hyporeflexia, spontaneous, ocular, or inducible clonus together with agitation, fever, diaphoresis, or muscle rigidity:

- Immediately interrupt epacadostat administration.
- Immediately interrupt any SSRI or SNRI administration.

- Provide appropriate medical management of the subject until all signs/symptoms are resolved (eg, IV fluids and/or sympathomimetic amines for hypotension, benzodiazepines for agitation, administration of 5-hydroxytryptamine antagonists such as cyproheptadine).
- If the subject chooses to remain in the study, restart treatment with epacadostat after the SSRI or SNRI has been discontinued no sooner than 5 half-lives have elapsed for the specific SSRI or SNRI in question and after resolution of signs/symptoms of SS. The SSRI or SNRI dosing MAY NOT be restarted.
- If the subject chooses to discontinue the study or must restart treatment with SSRI or SNRI, the subject should be scheduled for a follow-up visit. Selective serotonin reuptake inhibitor or SNRI treatment may be initiated 2 weeks after resolution of signs and symptoms of SS.

Table 27: Signs and Symptoms of Serotonin Syndrome

Tremor and hyporeflexia
Spontaneous clonus
Muscle rigidity, temperature > 38°C (100.4°F), and either ocular clonus or inducible clonus
Ocular clonus and either agitation or diaphoresis
Inducible clonus and either agitation or diaphoresis

5.4.4. Criteria for Permanent Discontinuation of Study Drug

The occurrence of unacceptable toxicity not caused by the underlying malignancy will be presumed to be related to study drug treatment and will require that the study drugs be permanently discontinued. Unacceptable toxicity is defined as follows:

- Occurrence of an AE that is related to treatment with the study drug that, in the judgment of the investigator or the sponsor's medical monitor, compromises the subject's ability to continue study-specific procedures or is considered to not be in the subject's best interest.
- An AE requiring more than 2 dose reductions.
- Persistent AE requiring a delay of therapy for more than 2 weeks (14 days) unless a greater delay has been approved by the sponsor.
- Concurrent elevation of ALT > 3 x ULN and total bilirubin > 2 x ULN in subjects who do not have evidence of biliary obstruction or other causes that can reasonably explain the concurrent elevations.

If study drug is permanently discontinued, see Sections 6.3 and 6.4 for follow-up assessments.

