5.4.1.2.2. Epacadostat Dose Modifications

[Table 11](#) describes epacadostat dose reductions that may occur due to any related AEs. Dose reductions should occur in a step-wise fashion from the initial starting dose of the cohort, and a maximum of 2 dose reductions of epacadostat are allowed for the management of an AE, regardless of the initial starting dose. If an AE recurs/does not return to baseline after the second

dose reduction of epacadostat, then the subject must permanently discontinue epacadostat. The lowest permissible dose of epacadostat is 25 mg BID. If a subject does not tolerate 25 mg BID, then the subject must permanently discontinue epacadostat.

Table 11: Epacadostat Dose Reductions

Dose Level
300mgBID
100mgBID
50mgBID
25 mgBID

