5.4.1.2.3. Azacitidine Dose Modifications

Table 12 describes azacitidine dose reductions that may occur due to any related AEs. Dose reductions should occur in a step-wise fashion from the initial starting dose of the cohort, and a maximum of 2 dose reductions of azacitidine are allowed for the management of an AE, regardless of the initial starting dose. If an AE recurs/does not return to baseline after the second dose reduction of azacitidine, then the subject must permanently discontinue azacitidine. The lowest permissible dose of azacitidine is 50 mg. If a subject does not tolerate 50 mg, then the subject must permanently discontinue azacitidine.

Table 12: Azacitidine Dose Reductions

Dose Level
100mg
75mg
50mg

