5.4.1.3. Procedures for Subjects Exhibiting Immune-Related Adverse Events

This section is meant to apply to suspected irAEs from epacadostat, pembrolizumab, or the combination.

Immune-related AEs may be defined as an AE of unknown etiology, associated with drug exposure and consistent with an immune phenomenon. Immune-related AEs may be predicted based on the nature of the pembrolizumab or epacadostat compounds, their mechanism of action, and reported experience with immunotherapies that have a similar mechanism of action. Special attention should be paid to AEs that may be suggestive of potential irAEs. An irAE can occur shortly after the first dose or several months after the last dose of treatment.

If an irAE is suspected, efforts should be made to rule out neoplastic, infectious, metabolic, toxin or other etiologic causes before labeling an AE as an irAE. Subjects who develop a Grade 2 irAE should be discussed immediately with the sponsor.

General recommendations to managing irAEs not detailed elsewhere in the Protocol are detailed in Table 18. Recommendations for management of specific immune-mediated AEs such as pneumonitis (Section 5.4.1.3.1), enterocolitis (Section 5.4.1.3.2), hepatitis (Section 5.4.1.3.3), dermatitis (Section 5.4.1.3.4), neuropathies (Section 5.4.1.3.5), endocrinopathies (Section 5.4.1.3.6), myocarditis (Section 5.4.1.3.7), and other immune-mediated AEs (Section 5.4.1.3.8) are detailed in the sections below.

Table 18: General Approach to Handling Immune-Related Adverse Events

irAE	Withhold/Discontinue Pembrolizumab and Epacadostat	Guidance for Restarting Study Treatment	Supportive Care
Grade 1	No action.	Not applicable.	Provide symptomatic treatment.
Grade 2	May withhold pembrolizumab and epacadostat per investigator's discretion.	May return to treatment if improves to Grade 1 or resolves within 6 weeks. If AE resolves within 4 weeks, subject may restart at the same dose and schedule for both pembrolizumab and epacadostat. For an AE that does not resolve within 4 weeks, epacadostat should be reduced 1 dose level, but pembrolizumab may be restarted at the same dose and schedule. If AE does not resolve within 6 weeks, study treatment with both study drugs should be discontinued or discussed with medical monitor.	Consider systemic corticosteroids in addition to appropriate symptomatic treatment.

Table 18: General Approach to Handling Immune-Related Adverse Events
 (Continued)

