5.5. Withdrawal of Subjects From Study Treatment

5.5.1. Withdrawal Criteria

Subjects must be withdrawn from study treatment for the following reasons:

- The subject becomes pregnant.
- Consent is withdrawn.
- Further participation would be injurious to the subject's health or well-being, in the investigator's medical judgment.
- The study is terminated by the sponsor.
- The study is terminated by the local health authority, IRB, or IEC.
- Unacceptable toxicity has occurred.
- Confirmed radiographic progression of disease per RECIST v1.1 (Eisenhauer et al 2009). See Section 5.4.2.
 - Note: For unconfirmed radiographic disease progression, see Section 5.4.2.
 - Note: A subject may be granted an exception to continue on treatment with confirmed radiographic progression if clinically stable or clinically improved. See Section 7.6.1.

A subject may be discontinued from study treatment as follows:

- If, during the course of the study, a subject is found not to have met eligibility criteria, the medical monitor, in collaboration with the investigator, will determine whether the subject should be withdrawn from the study.
- If a subject is noncompliant with study procedures or study drug administration in the investigator's opinion, the sponsor should be consulted for instruction on handling the subject.

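### When an adverse event outlasts two dose reductions of epacadostat or azacitidine, Protocol 5.4.4 and 5.5.1 end all study treatment, while 5.4.1.2.2 and 5.4.1.2.3 stop only that drug

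*Protocol*

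**What the plan says.** Protocol 5.4.4 lists what counts as unacceptable toxicity. One item is "An AE requiring more than 2 dose reductions", with no drug named. The stated consequence is that such toxicity "will require that the study drugs be permanently discontinued". Protocol 5.5.1 includes "Unacceptable toxicity has occurred" among the reasons for which withdrawal from study treatment is compulsory.

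The drug-specific sections differ. For epacadostat, 5.4.1.2.2 sets a "maximum of 2 dose reductions of epacadostat are allowed for the management of an AE". If the event persists or returns after the second, "then the subject must permanently discontinue epacadostat". Section 5.4.1.2.3 sets the same cap for azacitidine, and on the same failure "then the subject must permanently discontinue azacitidine". Neither section mentions stopping the remaining drugs.

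Other text assumes that one drug can be handled alone. Protocol 5.4.1.2 holds only the agent under suspicion and lets the other treatment go on. SAP 8.2.5 counts permanent discontinuation due to treatment-emergent AEs separately for epacadostat, azacitidine and pembrolizumab.

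**The concern.** Two mandatory instructions apply to one clinical event and lead to different places. Under one, the subject loses a single drug and stays on the others, with scheduled scans. Under the other, the subject stops everything and has an end-of-treatment visit. Sites reading different sections could treat like subjects differently.

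The analysis is affected through follow-up. Under Amendment 4, disease-status follow-up after treatment is no longer required (Synopsis, Study Schedule/Procedures; Protocol 5.5.2), and follow-up closes with the safety visit (4.4). Which rule a site follows can therefore change how long a subject is scanned, where PFS and DOR are censored, and whether a later response or progression is seen.

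**Working it through.** No planned figure is at issue. The check compares the texts, counts the dose ladders to see where the conflict can arise, and then traces the consequence.

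**Same trigger, different scope**

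| Text | Trigger | What stops |
|---|---|---|
| 5.4.1.2.2 | Event not settled after second epacadostat reduction | Epacadostat |
| 5.4.1.2.3 | Event not settled after second azacitidine reduction | Azacitidine |
| 5.4.4 with 5.5.1 | Event needing more than two reductions | All study treatment |

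Reductions are capped at two, so an event that has not settled after the second is one that would need a third. The triggers therefore coincide.

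**Where two reductions are possible**

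Inputs: Table 11 (epacadostat 300, 100, 50, 25 mg BID), Table 12 (azacitidine 100, 75, 50 mg) and the cap of two.

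Reductions available = min(2, number of levels below the starting dose). The conflict is reachable when this equals 2.

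| Drug and start | Levels below | Available | Reachable |
|---|---|---|---|
| Epacadostat 300 | 3 | min(2, 3) = 2 | yes |
| Epacadostat 100 | 2 | min(2, 2) = 2 | yes |
| Epacadostat 50 | 1 | min(2, 1) = 1 | no |
| Azacitidine 100 | 2 | min(2, 2) = 2 | yes |
| Azacitidine 75 | 1 | min(2, 1) = 1 | no |
| Azacitidine 50 | 0 | min(2, 0) = 0 | no |

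Mapped to Protocol Table 1, the epacadostat conflict can arise in Cohorts -1, 1, 2A, 2B and 3, but not in Cohort -2. The azacitidine conflict can arise only in Cohorts 2B and 3, and in any expansion at that dose.

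**Effect on the endpoints**

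1. Protocol Table 29 schedules tumor assessment on treatment and at end of treatment, but not at safety follow-up. This agrees with 5.5.2.
2. Protocol 7.6.1.2 still asks for imaging until progression, new anticancer treatment, consent withdrawal, death or study end. It was not aligned with 5.5.2.
3. In SAP Table 12, the rows for no progression and for discontinuation because of toxicity both censor PFS at the last valid scan. SAP 7.2.3 applies the same algorithm to DOR.
4. Under SAP 7.2.2 a CR or PR already recorded still counts. Only a response appearing after scanning stops would be missed, and the subject stays in the ORR denominator.

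**The case against.** The best defense is loose drafting. The heading and closing line of 5.4.4 use the singular for study drug, 5.4.1.2 favors holding only the suspected agent, and dose-reduction decisions are individual and made with the medical monitor. That may be what was meant, but it does not remove the conflict: the operative sentence is plural and 5.5.1 speaks of study treatment as a whole. Equally, that the other drugs continue under 5.4.1.2.2 and 5.4.1.2.3 is an inference from 5.4.1.2 and the SAP's per-drug counts, since those sections do not say it.

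Several stronger readings are tempting but not supported:

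- **Delays.** Section 5.4.4 also makes a delay beyond 14 days a permanent stop, while Table 18 says for Grade 2 "If AE resolves within 4 weeks, subject may restart at the same dose and schedule for both pembrolizumab and epacadostat". A reader might infer a second direct conflict. But 5.4.4 exempts delays the sponsor has approved. Section 5.4.1.2 tells the investigator to contact the sponsor before restarting after more than 14 days. Section 5.2.2.1 requires discussion with the medical monitor for such pembrolizumab delays, and 5.4.1.3 calls for immediate discussion of Grade 2 immune-related events. What remains is a wording gap between approval and discussion.
- **Azacitidine at any dose.** From 75 or 50 mg the ladder runs out before two reductions, so the drug-specific stop does not meet the 5.4.4 reduction criterion.
- **Treatment lost.** A reader might subtract the six azacitidine cycles from the 35 pembrolizumab administrations and call the difference the loss. That is a ceiling. Protocol 4.4 expects screening plus treatment to average about 6 months.
- **Imaging certainly lost.** Section 7.6.1.2 still asks for it, and the removal of follow-up comes from Amendment 4 and affects every subject off treatment, not only these.
- **Per-drug reporting absent.** SAP 8.2.5 and Appendix A Tables 3.2.13.1 to 3.2.13.3 already give discontinuation due to treatment-emergent AEs by drug.

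**Conclusion.** The contradiction stands and nothing in either document resolves it. It is limited to events that exhaust two reductions of epacadostat from a 100 or 300 mg BID start, or of azacitidine from a 100 mg start. This assumes reductions are counted per drug, which 5.4.4 does not say.

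The effect on results is possible censoring of PFS and DOR at the last valid scan, and a missed later response or progression, if all treatment stops and scanning ends. Its size cannot be stated because the documents give no rate for such events. Enrollment has stopped (SAP 5.2) and the Simon design will not be carried out (SAP 10.1.3), so the practical reach is subjects still on treatment and the interpretation of discontinuations already recorded. It is still worth correcting, because both rules are mandatory and the correction is nearly free.

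**What to change.** 1. Reconcile Protocol 5.4.4 and 5.5.1 with 5.4.1.2.2 and 5.4.1.2.3. For each 5.4.4 criterion, state whether it applies to one drug or to all study treatment. The clinical choice is the sponsor's.
2. Align 7.6.1.2 with 5.5.2 on whether imaging continues after treatment ends.
3. As a minor wording point, use one term for delays over 14 days where 5.4.4 asks for sponsor approval and 5.4.1.2 and 5.2.2.1 ask for discussion.
4. In SAP 6.2, at most add that discontinuation of study treatment means all drugs. No new table of AE-related discontinuation by drug is needed.

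The cost is a protocol clarification and one sentence in the SAP. Items 1, 3 and 4 need no extra data. Item 2 changes data collection only if the sponsor decides that scans should continue after treatment.

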5.5. Withdrawal of Subjects From Study Treatment

5.5.1. Withdrawal Criteria

Subjects must be withdrawn from study treatment for the following reasons:

- The subject becomes pregnant.
- Consent is withdrawn.
- Further participation would be injurious to the subject's health or well-being, in the investigator's medical judgment.
- The study is terminated by the sponsor.
- The study is terminated by the local health authority, IRB, or IEC.
- Unacceptable toxicity has occurred.
- Confirmed radiographic progression of disease per RECIST v1.1 (Eisenhauer et al 2009). See Section 5.4.2.
 - Note: For unconfirmed radiographic disease progression, see Section 5.4.2.
 - Note: A subject may be granted an exception to continue on treatment with confirmed radiographic progression if clinically stable or clinically improved. See Section 7.6.1.

A subject may be discontinued from study treatment as follows:

- If, during the course of the study, a subject is found not to have met eligibility criteria, the medical monitor, in collaboration with the investigator, will determine whether the subject should be withdrawn from the study.
- If a subject is noncompliant with study procedures or study drug administration in the investigator's opinion, the sponsor should be consulted for instruction on handling the subject.

5.5.2. Withdrawal Procedures

In the event that the decision is made to permanently discontinue the study drug, the end-of-treatment (EOT) visit should be conducted. Reasonable efforts should be made to have the subject return for a follow-up visit. These visits are described in Section 6. The last date of the last dose of study drug and the reason for subject withdrawal will be recorded in the eCRF.

If a subject is withdrawn from study treatment:

- The study monitor or sponsor must be notified.
- The reason(s) for withdrawal must be documented in the subject's medical record and in the eCRF.
- The EOT visit should be performed.

- The date of the EOT visit should be recorded in the eCRF and IRT.
- Subjects must be followed for safety until the time of the follow-up visit or until study dmG-related toxicities resolve, return to baseline, or are deemed irreversible, whichever is longest.

If the subject discontinues study treatment and actively withdraws consent for collection of follow-up data (safety follow-up or disease assessment), then no additional data collection should occur; however, subjects will have the option of withdrawing consent for study treatment but continuing in the follow-up period of the study for safety/efficacy assessments. Upon implementation of Amendment 4, disease assessment follow-up is no longer required.

5.6. Concomitant Medications

All concomitant medications and treatments must be recorded in the eCRF. Any prior medication received up to 30 days before the first dose of study dmG and 60 days after the last dose of study dmG will be recorded in the eCRF. Any addition, deletion, or change in the dose of these medications will also be recorded. Concomitant medications administered after 60 days after the last dose of study dmG should be recorded for SAEs as defined in Section 8. Concomitant treatments/procedures that are required to manage a subject's medical condition during the study will also be recorded in the eCRF.

5.6.1. Permitted Medications

All treatments that the investigator considers necessary for a subject's welfare may be administered at the discretion of the investigator in keeping with the community standards of medical care. All concomitant medication will be recorded on the eCRF, including all prescription, over-the-counter, herbal supplements, and IV medications and fluids. If changes occur during the study period, documentation of dmG dosage, frequency, route, and date may also be included on the eCRF.

Use of prophylactic growth factors should be based on American Society of Clinical Oncology guidelines for the use of white blood cell (WBC) growth factors (Smith et al 2006) and the investigator's clinical judgment. Bisphosphonates are allowed while subjects are receiving study treatment.

